## **Statement of Compliance**

The study will be carried out in accordance with Good Clinical Practice (GCP) as required by the following:

- United States Code of Federal Regulations (CFR) applicable to clinical studies (45 CFR Part 46; 21 CFR Part 50, 21 CFR Part 54, 21 CFR Part 56, and 21 CFR Part 312);
- International Conference on Harmonization (ICH) E6; 62 Federal Register 25691 (1997);

Compliance with these standards provides public assurance that the rights, safety and well-being of study subjects are protected, consistent with the principles that have their origin in the Declaration of Helsinki.

All key personnel (all individuals responsible for the design and conduct of this study) have completed Human Subjects Protection Training.

## List of Abbreviations

AE	Adverse Event
CFR	Code of Federal Regulations
CRF	Case Report Form
FDA	Food and Drug Administration
GCP	Good Clinical Practice
GRAS	Generally Recognized as Safe
ICF	Informed Consent Form
ICH	International Conference on Harmonisation
IRB	Institutional Review Board
LAR	Legally Authorized Representative
MedDRA	Medical Dictionary for Regulatory Activities
MOP	Manual of Procedures
N	Number (typically refers to subjects)
NOMC	New-Onset Medical Conditions
PI	Principal Investigator
SAE	Serious Adverse Event
SOP	Standard Operating Procedure
USP	United States Pharmacopeia

**Title:** **A Study to Evaluate the Safety, Reactogenicity and Acceptability of a Placebo Microneedle Patch in Healthy Infants and Young Children**

**Population:** Healthy infants and children, 6 weeks – 24 months inclusive

**Number of Sites:** One

**Study Duration:** Approximately 5 months

**Subject Duration:** Approximately 4 – 5 weeks

### **Objectives:**

#### **Primary:**

- To evaluate the safety and reactogenicity following application of a placebo microneedle patch topically.

#### **Secondary:**

- To evaluate unsolicited adverse events following application of a placebo microneedle patch topically.
- To evaluate new-onset medical conditions (NOMC) following application of a placebo microneedle patch topically.
- To evaluate the suitability of application of a placebo microneedle patch to different body locations.
- To evaluate the acceptability to the Legally Authorized Representative (LAR) of applying a placebo microneedle patch topically.

### **Endpoints**

#### **Primary:**

#### Safety:

- Occurrence of placebo microneedle patch-related serious adverse events from Day 1 through the Final Study Visit (Day 27 – 38).
- Occurrence of Grade 3 placebo microneedle patch-related solicited adverse events for the 8 days following application of the patch.

#### Reactogenicity:

- Occurrence of solicited application site reactogenicity (e.g., erythema, induration, bruising, itching) for the 8 days following application of the patch.

**Secondary:**

- Occurrence of Grade 3 placebo microneedle patch-related unsolicited adverse events from Day 1 through the Final Study Visit (Day 27 – 38).
- Occurrence of new-onset medical conditions (NOMC) from Day 1 through the Final Study Visit (Day 27 – 38).
- Occurrence of solicited and unsolicited adverse events described at the site at which the placebo microneedle patch was applied.
- Quantitative and qualitative description of LAR responses to survey questions.

**Schematic of Study Design:**

This is a single-center, unblinded, study in which healthy infants and children (6 weeks – 24 months inclusive) will have placebo microneedle patches applied to the skin. This study is designed to investigate the safety, reactogenicity, and acceptability of a placebo microneedle patch.

Infants and children will be enrolled into one of two possible cohorts that will have placebo microneedle patches administered topically for up to approximately 20 minutes. Cohort 1 will assess one formulation of the microneedle patch (Microneedle Formulation 1). If the Microneedle Formulation 1 is well tolerated in Cohort 1, Cohort 2 may be enrolled using a different formulation of the microneedle patch if available (Microneedle Formulation 2). Infants and children will be enrolled by sequential age groups using an age de-escalation approach (**Table 1**). At least 4 infants or children from each Group must complete Day 8 without halting criteria having been met (as detailed in Section 9.5) before subjects will be enrolled into the next younger age group within a Cohort. For Cohort 1, at least the first 2 children in each Group will have a microneedle patch initially applied to the skin overlying the shoulder blade. If this site is well tolerated without halting criteria having been met (as detailed in Section 9.5), additional microneedle patches may be applied to the same participants and in subsequent participants to the upper arm, forearm, wrist, thigh, shin, and/or foot. For Cohort 2, microneedle patches may be applied to the shoulder blade, upper arm, forearm, wrist, thigh, shin, and/or foot. If the first site is well tolerated in the first two children without halting criteria having been met (as detailed in Section 9.5), additional microneedle patches may be applied to the same participants and in subsequent participants.

Table 1: Cohorts and Groups of Enrolled Infants and Young Children			
Cohort	Group Age Range*	Number **	Study Product (administered Day 1 and possibly Day 8)
1	12 – 24 months	Up to 7	Microneedle formulation 1
1	5 – 11 months	Up to 6	Microneedle formulation 1
1	6 weeks – 4 months	Up to 12	Microneedle formulation 1
2	12 – 24 months	Up to 12	Microneedle formulation 2
2	5 – 11 months	Up to 12	Microneedle formulation 2
2	6 weeks – 4 months	Up to 12	Microneedle formulation 2

*\*All age ranges are inclusive. 4 children from each age group must complete Day 8 without halting criteria having been met (as detailed in Section 9.5) before subjects will be enrolled into the next younger age group.*

*\*\* Total number enrolled into each Cohort will be ≤25.*

Subjects will have an initial microneedle patch placed on Day 1. At Day 8, the LARs of subjects who have no ongoing solicited or unsolicited general AEs or local AEs will have the opportunity to decide to have second and third placebo microneedle patches placed at different body sites from the initial location.

Each subject will receive up to three placebo microneedle patches. Subjects will receive a first placebo microneedle patch on Day 1 and be assessed on Day 2 (+1 day), and Day 8 (+2 days). If the first patch is well tolerated without halting criteria having been met on Day 8 (+2 days), then the LAR will be provided the opportunity to have the subjects receive a second and third placebo microneedle patch on Day 8 and be assessed on Day 9 (+2 days) and Day 15 (+3 days). All subjects will have an end of study telephone call that will occur D27 – Day 38.

Safety will be measured by the occurrence of solicited application site and systemic reactogenicity on the day of microneedle patch administration through Day 8 for the first patch and through Day 15 (+3 days) for those that receive a second and third patch. If symptoms persist, clinic staff will attempt to follow up with the subject daily until two days symptom-free. Maximum severity post Day 8 (Day 15 in those that receive a second and third patch) and stop date of the symptoms will be recorded by clinic staff on the Solicited Events eCRF. Unsolicited AE, and serious adverse events (SAEs) and new-onset medical conditions (NOMC) will be collected through Day 27 and Day 38 after microneedle patch administration.

The acceptability of applying a microneedle patch topically will be assessed by LAR survey completed before each microneedle patch application, after microneedle patch removal, Day 2, and at Day 8 (+2 days) (and at Days 9 and 15 (+3 days) in those having an additional application).

## 2 BACKGROUND INFORMATION AND SCIENTIFIC RATIONALE

### 2.1 Background Information

Available vaccine delivery methods include intramuscular or subcutaneous injection using hypodermic needle which is limited by patient needle phobia (Hamilton 1995) and the need for trained medical personnel. Alternative routes of vaccination that avoid hypodermic needles have previously been poorly immunogenic, require live vaccines, utilize bulky devices and/or are unsuitable for self-administration (Mitragotri 2005, Kersten 2007). Novel vaccine delivery methods such as microneedles can render vaccination easier and more acceptable to the public by simplifying vaccine access, and can confer equal or superior immunological responses to that induced by hypodermic needle through conventional intramuscular administration (Kim 2012).

Microneedles are micron-scale needles that administer vaccine directly into the skin using a simple minimally invasive approach without generating sharps waste. The microneedles are solid conical structures made of water-soluble excipients that can encapsulate a vaccine. Excipients used will be on the Food and Drug Administration's (FDA) Generally Recognized as Safe (GRAS) list and/or on FDA's list of inactive ingredients in approved products. The microneedles that are used in the study are painlessly inserted into the skin as a patch with a hypoallergenic adhesive bandage backing. The microneedles are left in place for up to 20 minutes. During this time, the microneedles dissolve in the skin, so that upon removal of the patch, the microneedles have disappeared and the sharps-free patch backing can be discarded as non-sharps medical waste. Therefore, microneedle patch application can be carried out as simply as applying a Band-Aid® adhesive bandage.

Microneedles have been studied for vaccines including influenza, rabies, *Bacillus Calmette- Guerin (BCG)*, West Nile virus, and Human Papilloma Virus (HPV) (Kim 2012). There are a number of approved medical and cosmetic products using microneedles currently sold around the world. Soluvia® is a single hollow microneedle that is 1.5 mm long and is attached to a syringe (<http://www.bd.com/pharmaceuticals/products/microinjection.asp>). It is marketed worldwide prefilled with influenza vaccine for intradermal vaccination as IDflu®, Intanza® and Fluzone Intradermal®

(<http://www.fluzone.com/fluzone-intradermal-quadrivalent-vaccine.cfm>). Also MicronJet 600® received FDA clearance as a device (<http://www.nanopass.com/product/>).

Vaccination by microneedles is designed to increase patient compliance and access to immunization. In focus group studies of the public and healthcare professionals, microneedle patches were generally viewed positively compared to hypodermic needle injections (Birchall 2011). Perceived benefits included reduced pain, tissue damage and risk of infections, as well as possibility for self-administration. Concerns focused on delayed onset, cost, accurate and reliable dosing and the potential for misuse. In separate vaccination surveys associated with hollow microneedle injection of influenza vaccine, most physicians and the general public preferred microneedles over conventional intramuscular injection largely due to the smaller needle size, as well as the increased immunogenicity of intradermal vaccination (Arnou 2011). Physicians and patients alike thought that microneedle-based vaccination could increase vaccination coverage rates.

## 2.2 Rationale

Vaccines are typically injected using a hypodermic needle, a cost efficient, rapid and direct way for vaccine delivery. However, hypodermic needles cannot be easily used by patients themselves and patient willingness to receive vaccination is limited by pain and by needle-phobia experienced by many patients (Hamilton 1995). Spread of blood borne pathogens by needle re-use is also a major concern, especially in developing countries (Drucker 2001). Microneedles can be prepared as a low-cost patch that is simple for patients to apply for vaccine delivery targeting the many antigen-presenting cells present in the skin. A recent study at Emory University evaluated the safety, reactogenicity, acceptability, and immunogenicity of administration of influenza vaccine by microneedle patch in comparison to hypodermic needle injection. Data from this study demonstrated an excellent profile of the microneedle patch.

Data regarding the safety, reactogenicity, tolerability, and acceptability of a microneedle patch in children are lacking. The goal of this study is to evaluate the safety, reactogenicity, and acceptability of placement of a placebo microneedle patch to the skin of children. Twenty-five to 50 healthy children between the ages of 6 weeks and 24 months will be enrolled in the study. Subjects will be recruited from the general population of metro Atlanta, GA and enrolled at the Emory Children's Center, located on Emory University campus in Atlanta, GA.

#### *Skin irritation*

Microneedles can cause mild, transient skin irritation, primarily in the form of highly localized, mild and often punctuate erythema that disappears within hours or, in some cases, days. Erythema varies depending on length of microneedles. Bleeding is not characteristically seen. Itching has also been observed. Influenza vaccination using hollow microneedles has shown more local inflammatory reactions than hypodermic injection in human subjects. This may be due to inflammatory reactions being more easily visible in the skin than those that may occur after intramuscular injection (Arnou 2009).

#### *Skin infection*

There have been no reports of skin infection with microneedle insertions in thousands of people and animals (Kim 2012).

#### *Adhesive backing component*

The adhesive backing component is made from hypoallergenic material (commercial 3M medical tapes designed to adhere to skin). Local reactions (e.g., erythema, itching) can occur rarely, particularly with removal of the adhesive from the skin.

### *Placebo Microneedle Patch and Excipients*

Excipients (inactive ingredients) used to make the microneedles will be USP-grade and listed on FDA's database of Inactive Ingredients for Approved Drug Products. The final composition of the patch for Cohort 1 and Cohort 2 has not been finalized but all excipients are already in use in FDA-approved drug products (and usually at a much higher dose than will be used in the microneedle patch). Excipients are expected to include trehalose, sorbitol, histidine, maltodextrin, sodium carboxymethylcellulose, polysorbate, xylitol, polyvinyl alcohol, and/or glycerol. The total mass of excipients delivered by placebo microneedle patch will be <1.5 mg.

The microneedle patches used in the placebo study will be manufactured under low bioburden conditions and in compliance with cGMP requirements for Phase 1 clinical trials according to the *FDA's Guidance for Industry 2008: CGMP for Phase 1 Investigational Drugs*. This will be the same process and same controls as those used in the manufacture of microneedle patches investigated in the Phase 1 clinical trial of the microneedle patch for influenza vaccination carried out by Georgia Tech and the Hope Clinic.

The microneedle patch has a history of safe use in human subjects. It has been used in several IRB-approved studies at Georgia Tech in adults and has always exhibited a safe profile that typically consists of itching and/or mild erythema that subsides after a few days. Similarly, the Phase 1 trial of the microneedle patch for influenza vaccination showed that the microneedle patch was safe with no serious adverse events (SAEs) reported. No new chronic medical illnesses or influenza-like illnesses were reported with the patch.

Although the composition of the microneedle patches used in these studies was different from that of the patches for the proposed placebo study in infants and young children, the microneedle patches were made of excipients that had the same safety profile as those that will be used in this placebo study. The controls that will be used to make the infant and young children placebo patches will be at least as strict as those that were used to make the patches used in the Georgia Tech IRB studies and the initial Phase 1 clinical trial of influenza vaccine administration by microneedle patch.

### **2.3.2 Known Potential Benefits**

The knowledge gained from this study will facilitate the design of more effective and acceptable methods for administering vaccines in children by use of a microneedle patch. A future clinical trial of the microneedle patch for inactivated poliovirus (IPV) vaccination in infants is planned to occur in 2018, and the results from this IRB study will inform the design of this future clinical trial and others. There is no direct benefit to study participants.

## 3 OBJECTIVES

### 3.1 Study Objectives

#### 3.1.1 Primary Objectives

- To evaluate the safety and reactogenicity following application of a placebo microneedle patch topically.

#### 3.1.2 Secondary Objectives

- To evaluate unsolicited adverse events following application of a placebo microneedle patch topically.
- To evaluate new-onset medical conditions (NOMC) following application of a placebo microneedle patch topically.
- To evaluate the suitability of application of a placebo microneedle patch to different body locations.
- To evaluate the acceptability to the Legally Authorized Representative (LAR) of applying a placebo microneedle patch topically.

### 3.2 Study Endpoints

#### 3.2.1 Primary Endpoints

##### Safety:

- Occurrence of placebo microneedle patch-related serious adverse events from Day 1 through the Final Study Visit (Day 27 – 38).
- Occurrence of Grade 3 placebo microneedle patch-related solicited adverse events for the 8 days following application of the patch.

##### Reactogenicity:

- Occurrence of solicited application site reactogenicity (e.g., erythema, induration, bruising, itching) for the 8 days following application of the patch.

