Infants and children will be enrolled by sequential age groups using an age de-escalation approach (Table 1). At least 4 infants or children from each Group must complete Day 8 without halting criteria having been met (as detailed in Section 9.5) before subjects will be enrolled into the next younger age group within a Cohort. For Cohort 1, at least the first 2 children in each Group will have the microneedle patch applied to the skin overlying the shoulder blade. If this site is well tolerated without halting criteria having been met (as detailed in Section 9.5), additional microneedle patches may be applied at a different location on the same participant and in subsequent participants to the upper arm, forearm, wrist, thigh, shin, and/or foot. For Cohort 2, microneedle patches may be applied to the

shoulder blade, upper arm, forearm, wrist, thigh, shin, and/or foot. If the first site is well tolerated in the first two children without halting criteria having been met (as detailed in Section 9.5), additional microneedle patches may be applied to the same participants and in subsequent participants.

Table 1: Cohorts and Groups of Enrolled Infants and Young Children			
Cohort	Group Age Range*	Number **	Study Product (administered Day 1 and possibly Day 8)
1	12 – 24 months	Up to 7	Microneedle formulation 1
1	5 – 11 months	Up to 6	Microneedle formulation 1
1	6 weeks – 4 months	Up to 12	Microneedle formulation 1
2	12 – 24 months	Up to 12	Microneedle formulation 2
2	5 – 11 months	Up to 12	Microneedle formulation 2
2	6 weeks – 4 months	Up to 12	Microneedle formulation 2

*\*All age ranges are inclusive. 4 children from each age group must complete Day 8 without halting criteria having been met (as detailed in Section 9.5) before subjects will be enrolled into the next younger age group.*

*\*\* Total number enrolled into each Cohort will be ≤25.*

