### **8.1.5 Reactogenicity**

The LAR will be provided with a memory aid, thermometer and ruler and will be instructed to record the presence of solicited symptoms and oral temperature through the Day 8 (+2 days) (Day 15 +3 days in those having microneedle patches 2/3 placed).. If a symptom is still present at that time, the LAR will continue to follow that symptom until two days symptom-free. Memory aids will be reviewed and collected by study staff at follow-up visits.

Solicited local microneedle patch application site symptoms include:

- Pain
- Erythema
- Ecchymosis (bruising)
- Induration/swelling
- Pruritus (itching)
- Tenderness

Solicited systemic reactions include:

- Fever
- Irritability (fussiness) above baseline
- Lethargy (drowsiness)
- Decreased appetite
- Vomiting

The LAR will use the following grading scale for describing symptoms:

- Grade 0: Not present
- Grade 1: Mild (present but easily tolerated)
- Grade 2: Moderate (able to tolerate routine activity with effort)
- Grade 3: Severe (unable to continue routine activity)

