## 9.5 Study Halting Rules

Further enrollment and placebo microneedle patch application (e.g., placebo microneedle patch 2/3 placement) to subjects will be halted if any of the following occur:

- Any death following placebo microneedle patch application.
- Any subject develops erosion, ulceration, or abscess at the administration site related to study product administration.
- Any subject develops laryngospasm, bronchospasm or anaphylaxis within 24 hours of placebo microneedle patch administration.
- Any subject experiences a placebo microneedle patch-related SAE.
- Any Grade 3 AEs or an SAE that cannot be clearly attributed to another cause.

If the study is halted, the site will immediately notify the Sponsor and the Emory IRB. Prior to recommencing enrollment, all available safety data will be reviewed by the site Investigator and the Sponsor.

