## 14.2 Appendix B: Adverse Event & Reactogenicity Grading - LOCAL SITE REACTIONS

	LOCAL SITE REACTIONS			
	Grade			
	0	1	2	3
Induration/ Swelling *	None to less than 2.5 cm	2.5 – 5 cm and does not interfere with activity	5.1 – 10 cm or interferes with activity	> 10 cm or prevents daily activity, erosion, or ulceration
Erythema**	None to less than 2.5 cm	2.5 – 5 cm	5.1 – 10 cm	> 10 cm, erythroderma, or a diffuse rash >15% of the body surface area
Ecchymosis	None	2.5 – 5 cm	5.1 – 10 cm	> 10 cm
Tenderness	None	Mild discomfort to touch	Discomfort with movement	Significant discomfort at rest
Pain	None	Does not interfere with activity	Repeated use of non-narcotic pain reliever > 24 hours or interferes with activity	Any use of narcotic pain reliever or prevents daily activity
Pruritus (Itching)	None	Mild	Moderate itching; limiting instrumental activities of daily living	Severe itching; limiting self-care activities of daily living

\*Induration/swelling should be evaluated and graded using the functional scale as well as the actual measurement

\*\*In addition to grading the measured local reaction at the greatest single diameter, the measurement should be recorded as a continuous variable.

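### Patch-site erosion, ulceration or abscess halts the study and gates age de-escalation, but the solicited list and the caregiver's grading scale contain no explicit prompt for them

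*Combined protocol and SAP*

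**What the plan says.** The reactogenicity endpoint in Sections 3.2.1 and 11.1, "Occurrence of solicited application site reactogenicity (e.g., erythema, induration, bruising, itching) for the 8 days following application of the patch", gives examples only. The working list is in Section 8.1.5, under "Solicited local microneedle patch application site symptoms include": pain, erythema, ecchymosis, induration/swelling, pruritus and tenderness. The LAR receives a memory aid, thermometer and ruler, and grades symptoms on a generic functional scale whose top level is "Grade 3: Severe (unable to continue routine activity".

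One of the study halting rules in Section 9.5 reads "Any subject develops erosion, ulceration, or abscess at the administration site related to study product administration". Section 4 ties age de-escalation to those rules: "At least 4 infants or children from each Group must complete Day 8 without halting criteria having been met".

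Under Sections 9.2 and 9.2.2, safety parameters are graded, and reactogenicity analyzed, with Appendices B and C. In Appendix B, Grade 3 induration/swelling is "> 10 cm or prevents daily activity, erosion, or ulceration". No other cell mentions erosion or ulceration, and there is no row for abscess or infection. Section 2.3.1 gives skin infection its own heading among the potential risks, and adds: "There have been no reports of skin infection with microneedle insertions in thousands of people and animals".

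Sites are checked 15 and 30 minutes after patch removal and examined on Day 2 (+1) and Day 8 (+2). After patches 2/3 they are also examined on Day 9 (+2) and Day 15 (+3) (Sections 7.1 to 7.5). At the follow-up visits staff take an interim history, review the memory aid and record AEs. Rash, scarring or signs of infection at the site go to an investigator. Section 9.2.1 has AE details collected by LAR interview. Section 9.2.2 adds memory-aid review for reactogenicity and says that the memory aid is not source.

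**The concern.** The site events with the greatest consequence in this protocol have no item of their own in the caregiver's daily record, whereas redness and itching do. A related erosion or ulceration graded under the induration row is a Grade 3 solicited event, and so counts in the primary safety endpoint. It can meet two halting criteria: the site-lesion rule, and the rule on Grade 3 AEs not clearly attributed to another cause.

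The two scales also point in different directions. An active infant with a small erosion carries on with routine activity, so the LAR's scale leads to Grade 0 or 1, where Appendix B gives Grade 3. The investigator assigns the severity of AEs (Section 9.2.1), so the LAR's score need not be final. It is, however, part of the record reviewed at the interview, and a 0 or 1 gives staff little reason to ask further.

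At stake is how much weight a result of no erosion or abscess can bear, both at the gate to a younger group and in the final report.

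**Working it through.** **1. Coverage of each lesion**

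| Event | Halts under 9.5 | Solicited item in 8.1.5 | Named in LAR scale | Appendix B |
|---|---|---|---|---|
| Erosion, ulceration | Yes, if related | No item of its own | No | Only within Grade 3 induration/swelling |
| Abscess | Yes, if related | No | No | No row |
| Skin infection | Not named | No | No | No row |

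An erosion without swelling therefore has no clear row.

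**2. Days without a clinic examination, within Days 1–8 after patch 1**

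- Visits on Days 1, 2 and 8 leave Days 3–7: 5 days.
- Visits on Days 1, 3 and 8 leave Day 2 and Days 4–7: 5 days.
- Visits on Days 1 and 2, then Day 9 or 10, leave Days 3–8: 6 days.
- Visits on Days 1 and 3, then Day 9 or 10, leave Day 2 and Days 4–8: 6 days.

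The range is 5 to 6 of 8 days. After patches 2/3 the nominal gap is Days 10–14. Children with one patch have no scheduled examination after the Day 8 (+2) visit, only the telephone call.

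**3. The plan's own detection figures**

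The plan gives no figure for capture of lesions. Section 11.2 gives chances of observing AEs with 25 subjects. At a 5% rate it states 34% for one and 12% for more; the exact binomial at n = 25 gives 25 × 0.05 × 0.95^24 = 36.5% and 35.8%. At 10% it states 38% and 34%, against 19.9% and 72.9%. All four stated figures match n = 12 instead (34.1%, 11.8%, 37.7%, 34.1%). That is a separate discrepancy, and nothing below uses those figures.

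**4. Illustration of the loss**

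Let t be the true lesion rate per child, h the share of lesions healed before the next examination, and q the share of those that is still reported. If examination finds every persisting lesion, the captured share is c = 1 − h(1 − q). The chance that at least one of n children shows a recorded lesion is 1 − (1 − tc)^n. The gate gives n = 4. The documents give none of t, h or q; all are assumed. With h = 1 (worst case), c = q:

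| t | c = 1 | c = 0.75 | c = 0.5 |
|---|---|---|---|
| 10% | 34.4% | 26.8% | 18.5% |
| 5% | 18.5% | 14.2% | 9.6% |
| 0.3% | 1.2% | 0.9% | 0.6% |

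For example, at t = 5%: 1 − 0.95^4 = 18.5%, and 1 − 0.975^4 = 9.6%. If only half of the lesions heal before examination and half of those are reported, c = 1 − 0.5 × 0.5 = 0.75, and the figure is 14.2%. For a full cohort of 25 at t = 5%, the chance falls from 72.3% at c = 1 to 46.9% at c = 0.5.

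The 0.3% row is 3/1,000, the rule-of-three bound if the statement in Section 2.3.1 is read as zero infections in 1,000 exposures. That count is an assumption, and the statement covers infection only and mixes people with animals.

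**The case against.** A reader might infer that none of these lesions is solicited, and that between visits they are recorded only if the LAR volunteers them. The documents support neither reading. Erosion and ulceration are Grade 3 criteria of a solicited item. Staff take an interim history, interview the LAR and examine the site at each follow-up clinic visit, including Day 8, which gate children must complete. Unscheduled visits also include a site examination (Section 7.8), and unsolicited events at the patch site are already a secondary endpoint. Nor does infection itself halt the study: Section 9.5 names erosion, ulceration and abscess.

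It is also fair to say that the illustration is a worst case. The lesion would have to appear and heal within about five days and go unmentioned at interview. An abscess in particular would probably cause swelling, redness, tenderness or fever, all of which are solicited. Section 2.3.1 suggests that infection is rare.

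All of this narrows the point but does not remove it. A general question about changes since the last visit is not a daily, item-specific prompt. A small erosion need not cause swelling or limit an infant's activity. The mismatch between the LAR's scale and Appendix B remains whatever the lesion rate.

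**Conclusion.** The point holds as a gap in prompting, not as an absence of collection. Persisting lesions should be found at the clinic examinations. Those that start and heal on the 5 or 6 days without one depend on unprompted recall at interview, and a small one may score 0 or 1 on the LAR's scale although Appendix B makes erosion Grade 3.

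The size of the loss cannot be derived from the documents. At an assumed 5% rate with half captured, detection among four gate children falls by 8.9 percentage points (18.5% to 9.6%). This is an upper bound for that rate and reporting share, because it lets every lesion heal before examination. At 0.3% the fall is 0.6 points; at 10% it is 15.8. None of these figures shows that the gate is unsafe.

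The memory aid and the manual of procedures are not among the documents, so the prompts actually used cannot be checked. The case for change rests on the low cost of the remedy and on the role of these lesions in stopping, gating and the primary safety endpoint.

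**What to change.** First confirm that the memory aid does not already carry such a line. If it does not:

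- Add one prompted yes/no line per patch site to Section 8.1.5, the memory aid and the Solicited Events eCRF: *blister, open skin, or pus/discharge*, with start and stop dates.
- Have staff check each positive answer against the existing wording of Appendix B and Section 9.5. The line is a screening question and is wider than the halting criterion (blister, for instance, is not in Section 9.5), so a positive answer is not in itself a halting event.
- Report it as a separate row under the reactogenicity endpoint (Sections 3.2.1 and 11.1) and the body-site endpoint (Section 3.2.2).

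The halting rule and the visit schedule stay as they are. The cost is one memory-aid line, one eCRF field and one table row, plus a few trivial positive answers for staff to check.
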